8.6. Safety Analysis

All safety data collected on or after the date that study drug was first dispensed up to the date of last dose of study drug plus 30 days will be summarized for the Safety Analysis Set by cohort and overall. Data for the pretreatment period and after date of last dose of study drug plus 30 days will be included in data listings.

Descriptive summaries will be provided for the primary safety endpoints of incidence of treatment-emergent AEs and treatment-emergent laboratory abnormalities. No formal statistical testing is planned.

8.6.1. Extent of Exposure

A participant's extent of exposure to study drug data will be generated from the study drug administration data. Exposure data will be summarized by cohort and overall.

8.6.2. Adverse Events

Clinical and laboratory AEs will be coded using the current version of the MedDRA. System organ class, high-level group term, high-level term, preferred term, and lower-level term will be attached to the clinical database.

Events will be summarized on the basis of the date of onset for the event. A treatment-emergent AE will be defined as any AE that begins on or after the date of first dose of study drug up to the date of last dose of study drug plus 30 days.

Summaries (number and percentage of participants) of treatment-emergent AEs (by system organ class and preferred term) will be provided by cohort and overall.

8.6.3. Laboratory Evaluations

Selected laboratory test data (using conventional units) will be summarized using observed data. Data and change from baseline at all scheduled time points will be summarized.

Graded laboratory abnormalities will be defined using the grading scheme in DAIDS Table for Grading the Severity of Adult and Pediatric Adverse Events, Version 2.1 (corrected, July 2017). The DAIDS scale is available at:

<https://rsc.niaid.nih.gov/sites/default/files/daidsgradingcorrectedv21.pdf>

Incidence of treatment-emergent laboratory abnormalities, defined as values that increase at least 1 toxicity grade from baseline at any time postbaseline up to 30 days after the date of the last dose of study drug, will be summarized by cohort and overall. If baseline data are missing, then any graded abnormality (ie, at least a Grade 1) will be considered treatment emergent.

Laboratory abnormalities that occur before the first dose of study drug or after the participant has been discontinued from treatment for at least 30 days will be included in a data listing.

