- ODV CCI administered orally twice daily for participants aged \geq 6 years to < 18 years and weighing \geq 40 kg (Cohort 1).
- ODV CCI administered orally twice daily for participants aged \geq 6 years to < 18 years and weighing \geq 20 kg to < 40 kg (Cohort 2).

Reference Therapy, Dose, and Mode of Administration: Not applicable

Duration of Intervention: 5 days

Study Procedures/Frequency:

- Screening: within 48 hours of the baseline (Day 1) visit (screening and baseline visits may occur on the same day)
- Study treatment period: 5 days
 - In-person visits at Days 1 and 5
 - In-person or remote visit at Day 3
- Posttreatment follow-up period: 30 days after the last dose of study drug
 - In-person or remote visits at Days 8 and 14
 - Virtual visits at Days 21 and 28
 - End-of-study in person visit at Day 35

[Table 1](#) outlines the schedule of study procedures.

Statistical Methods:

Safety: Treatment-emergent AEs and selected laboratory test data will be summarized using descriptive statistics and listed by participant. The proportion of participants with concomitant use of medications other than RDV and ODV for treatment of COVID-19 will be provided in summary tables by cohort and overall. Palatability and acceptability will be summarized using descriptive statistics by cohort and overall.

[figure not shown]
Pharmacokinetics: Plasma concentrations and PK parameters will be listed and summarized for GS-441524 using descriptive statistics by cohort and overall.

Efficacy: The efficacy endpoints will be summarized using descriptive statistics and listed by participant.

Sample Size: A minimum of 12 evaluable participants from each cohort (Cohorts 1-4) provides > 90% power to reject the null hypothesis that there is at least a 30% difference in GS-441524 AUC₀₋₁₂ and C_{max}, respectively, between pediatric and adult participants, using 2 one-sided tests with each performed at an alpha level of 0.05. This power analysis assumes that the expected geometric mean ratio between the pediatric participants versus the adult group is 1, the equivalency boundary is 70% to 143%, and the interparticipant standard deviations of AUC₀₋₁₂ and C_{max} are 0.19 h•ng/mL and 0.18 ng/mL (natural log scale, preliminary results from Study GS-US-611-6248).

STUDY SCHEMA

Figure 1. Study Schema

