2. OBJECTIVES AND ENDPOINTS

Primary Objectives	Primary Endpoints

• To evaluate the plasma PK of ODV in pediatric participants with COVID-19• To evaluate the safety and tolerability of ODV in pediatric participants with COVID-19	
• PK parameters (AUC₀₋₁₂, C_{max}, and C_{trough}) for ODV metabolite, GS-441524• Incidence of treatment-emergent AEs by Day 35• Incidence of treatment-emergent laboratory abnormalities by Day 35
Secondary Objectives	Secondary Endpoints

• To assess the impact of ODV on time to sustained alleviation of targeted COVID-19 symptoms in pediatric participants with COVID-19• To evaluate the antiviral activity of ODV on SARS-CoV-2 nasal swab viral load in pediatric participants with COVID-19• To assess the impact of ODV on the requirement for supplemental oxygen in pediatric participants with COVID-19• To evaluate palatability and acceptability of ODV in pediatric participants with COVID-19• To provide data on the use of medications other than RDV and ODV for treatment of COVID-19 in pediatric participants with COVID-19• To assess the impact of ODV on COVID-19-related hospitalizations or all-cause death in pediatric participants with COVID-19	
• Time to sustained alleviation of targeted COVID-19 symptoms by Day 35• Change from baseline in SARS-CoV-2 nasal swab viral load at Day 5• Proportion of participants who require supplemental oxygen support (low flow oxygen, high flow oxygen, noninvasive ventilation, mechanical ventilation, or extracorporeal membrane oxygenation) by Day 35• Assessment of palatability and acceptability scores of each formulation at Day 5• Proportion of participants with concomitant use of medications other than RDV and ODV for treatment of COVID-19 by Day 35• Proportion of participants with COVID-19-related hospitalization or all-cause death by Day 35

CCI

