3.2. Duration of Intervention

Duration of dosing is 5 days.

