6.3.2.4. Clinical Laboratory Assessments

Refer to [Table 1](#) for clinical laboratory assessment time points.

Following laboratory assessments will be performed:

- Hematology: Complete blood count (CBC) with differential
- Comprehensive metabolite panel (Chemistry 14): ALT, albumin, alkaline phosphatase, aspartate aminotransferase (AST), total bilirubin (and neonatal bilirubin for participants aged <14 days and participants presenting with jaundice), blood urea nitrogen and creatinine

(include BUN:Cr ratio, and eGFR using bedside Schwarz formula if \geq 1 year of age), ionized calcium, carbon dioxide, chloride, total serum protein, potassium, sodium

- Urinalysis

The smallest possible blood vials, such as microtainer tubes, must be used for participants weighing < 15 kg.

Clinical laboratory assessments at other days may be conducted if required by clinical need or local practice. The results of all clinical laboratory tests that are performed as part of clinical care, even if not required by the protocol, should be reported.

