7.3.2. Adverse Events

Following initiation of study drug, collect all AEs, regardless of cause or relationship, until 30 days after last administration of study drug and report the AEs on the eCRFs as instructed.

All AEs and clinically significant laboratory abnormalities should be followed until resolution or until the AE is stable, if possible. Gilead may request that certain AEs be followed beyond the protocol-defined follow-up period.

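### An end-of-study laboratory sample taken on Days 36 to 40 is within the allowed visit window but falls outside the primary laboratory endpoint, which closes 30 days after the last dose.

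*Protocol*

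**What the plan says.** The primary laboratory endpoint in Protocol Section 2 is "Incidence of treatment-emergent laboratory abnormalities by Day 35". Section 8.6.3 defines a treatment-emergent abnormality as a rise of at least one toxicity grade from baseline "at any time postbaseline up to 30 days after the date of the last dose of study drug". Section 8.6 applies the same limit to all safety summaries: "Data for the pretreatment period and after date of last dose of study drug plus 30 days will be included in data listings". Section 8.3.1.2 likewise takes in data from treatment plus 30 days.

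On timing, Section 3.2 states "Duration of dosing is 5 days", and the synopsis gives "Posttreatment follow-up period: 30 days after the last dose of study drug". Table 1 sets the end-of-study visit at Day 35 with a window of 5 days either side. Table 5 (Section 11.6, Cohorts 1 and 2) schedules hematology and chemistry at Screening/Day 1, Day 3, Day 5 and Day 35/EOS.

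Section 8.6.3 ends by saying that laboratory abnormalities arising "after the participant has been discontinued from treatment for at least 30 days will be included in a data listing".

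**The concern.** The analysis window closes on the nominal day of the last visit, but the visit may take place up to five days later. A site that keeps to the visit schedule can thus produce a sample that the analysis rule discards. In Cohorts 1 and 2 that sample is the only scheduled hematology and chemistry result after Day 5, and it belongs to a primary endpoint. The protocol contains no rule that assigns a late but in-window sample to Day 35.

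Three things are at stake:

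- Whether a participant contributes a follow-up laboratory result depends on the appointment date and not on anything clinical.
- For someone who stops drug early the limit moves earlier with the last dose, so a sample taken exactly on Day 35 is excluded from an endpoint that runs to Day 35.
- The two sentences in Section 8.6.3 disagree about a result exactly 30 days after the last dose. For a full course that is Day 35, the nominal visit day.

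**Working it through.** **Inputs**

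- Dosing lasts 5 days (Section 3.2), so the planned last dose is on Day 5.
- The laboratory limit is last dose + 30 days (Sections 8.6 and 8.6.3).
- The end-of-study window is Day 35 ± 5 (Table 1), that is Days 30 to 40: 40 − 30 + 1 = 11 days.
- Scheduled hematology and chemistry draws after Day 1 are on Day 3, Day 5 and Day 35/EOS (Table 5).
- The distribution of actual visit days is not in the document and has to be assumed.

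**The plan's own figure.** 5 + 30 = 35, so the Day 35 in the endpoint is reproduced for a last dose on Day 5.

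**Allowed visit days after the limit.** For last dose on Day L, the limit is L + 30 and the number of excluded days is 40 − (L + 30) = 10 − L.

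| Last dose | Limit | Excluded end-of-study days | Share of 11 days |
|---|---|---|---|
| Day 5 | Day 35 | 5 | 45% |
| Day 4 | Day 34 | 6 | 55% |
| Day 3 | Day 33 | 7 | 64% |
| Day 2 | Day 32 | 8 | 73% |
| Day 1 | Day 31 | 9 | 82% |

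For any last dose on Day 4 or earlier, Day 35 itself lies after the limit. If an evening start pushed the last dose to Day 6 (an assumption), the limit would be Day 36 and 4 of 11 days would be excluded.

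**Expected share of full-course samples lost.** Give visit day d the weight w(d) ∝ exp(−½((d − 35)/s)²) for d = 30 to 40, and sum the normalised weights over Days 36 to 40:

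- s = 1 day: 30%
- s = 2 days: 40%
- s = 3 days: 43%
- even spread over the window: 5/11 = 45%
- all visits on or before Day 35: 0%

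At 30% to 45%, a cohort of 12 loses about 4 to 5 samples (12 × 0.301 = 3.6; 12 × 5/11 = 5.5). Cohorts 1 and 2 together, at the minimum of 24, lose about 7 to 11 (7.2 to 10.9). If the later cohorts receive the same draw schedule, 52 participants lose about 16 to 24 (15.6 to 23.6).

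**The boundary.** A result 30 days after the last dose satisfies "at any time postbaseline up to 30 days after the date of the last dose of study drug" and so counts. It is also 30 days after treatment ended, so "after the participant has been discontinued from treatment for at least 30 days will be included in a data listing" sends it to a listing. If the second sentence governs, Day 35 is lost too, and 6 of 11 days (55%) are excluded for a full course.

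**After the change.** If the laboratory period runs through the in-window end-of-study visit, 0 of 11 days are excluded for every last-dose day. A fixed limit of last dose + 35 days would also give 0 for a full course, but would still exclude 1, 2, 3 or 4 days for a last dose on Day 4, 3, 2 or 1.

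**The case against.** A fixed 30-day risk period is a defensible choice and fits the Day 35 endpoint. The safety analysis is descriptive, excluded values still appear in listings, and Day 3 and Day 5 samples still count. Section 1.2.1.2.1 gives an adult median half-life for GS-441524 of 6 to 7 hours, so Day 36 lies more than 100 half-lives after a Day 5 dose (31 × 24 / 7 ≈ 106). All of this stands and limits the harm. It does not justify the cut, however: Day 35 is also more than 100 half-lives out (30 × 24 / 7 ≈ 103), yet the plan schedules a draw there and counts it.

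Unscheduled results may add data: "Clinical laboratory assessments at other days may be conducted if required by clinical need or local practice". They are not required, so they do not replace the scheduled sample. Table 5 covers Cohorts 1 and 2 only, and the tables for later cohorts are deferred to an amendment. A statistical analysis plan could add visit mapping, but the protocol itself fixes the limit.

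Three stronger readings are tempting and are not supported:

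- *A reader might infer that late visits cause adverse events to be under-counted.* Section 8.6.2 classifies adverse events by onset date, so a visit on Day 38 can still record an event that began by Day 35.
- *A reader might infer that an end-of-study visit on Days 30 to 34 ends adverse event collection early.* Section 7.3.2 requires collection "until 30 days after last administration of study drug" whatever the visit date, and Section 7.3.3 expressly covers serious events and deaths between that visit and 30 days after the last dose.
- *A reader might infer that early stoppers are left with no post-treatment laboratory data.* Section 6.4.1 asks that they continue study procedures. A last dose on Day 1 or 2 leaves the Day 3 and Day 5 draws after treatment, and a last dose on Day 3 or 4 leaves the Day 5 draw. These count. The 55% to 82% shares describe the end-of-study draw alone.

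**Conclusion.** The point holds for laboratory values. The limit in Sections 8.6 and 8.6.3 and the window in Table 1 do not fit together, and a protocol-compliant sample on 5 of the 11 allowed days drops out of a primary safety endpoint. The count of days follows from the document. The 30% to 45% share of full-course samples does not: it rests on visits being spread evenly over the window or centred on Day 35, and could be 0%. For anyone whose last dose is on Day 4 or earlier, the definition contradicts the endpoint, because an on-time Day 35 sample is left out.

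The endpoint loses part of its follow-up information, not all its data. The overlap at exactly 30 days is a drafting error. Sections 8.6 and 8.3.1.2 both favour including that day, but it falls on the nominal visit day and should not be left to interpretation.

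**What to change.** In Sections 8.6 and 8.6.3, count laboratory results through the later of last dose plus 30 days and the in-window end-of-study visit, and map that visit to Day 35. In the last sentence of Section 8.6.3, replace the at-least-30-days condition with more than 30 days, subject to the same end-of-study exception. Make any analysis plan wording match.

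Tie the rule to the visit rather than to a fixed last dose plus 35 days, which would still lose some early stoppers' samples. Leave the adverse event period at last dose plus 30 days and the visit window as it is. Extending the adverse event period would conflict with the Day 35 endpoint, and changing the visit window is not needed to recover these samples.

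The cost is wording only, with no added visits or blood draws. The downside is that a few laboratory values up to 5 days past Day 35 will be counted. For early stoppers these lie further from the last dose, at most 39 days (Day 40 after a last dose on Day 1). Reported incidence may rise slightly.

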8.6.4. Other Safety Evaluations

The proportion of participants with concomitant use of medications other than RDV and ODV for treatment of COVID-19 will be provided in summary tables by cohort and overall.

Palatability and acceptability will be summarized using descriptive statistics by cohort and overall.

8.7. Adjustments for Multiplicity

No adjustments for multiplicity are planned for this study.

8.8. Pharmacokinetic Analysis

For all PK analyses, the PK Analysis Set will be used.

Plasma concentrations and PK parameters will be listed and summarized for GS-441524 using descriptive statistics by cohort and overall.

8.9. Sample Size

The total sample size will be at least 52 participants.

A minimum of 12 evaluable participants from each cohort (Cohorts 1-4) provides > 90% power to reject the null hypothesis that there is at least a 30% difference in GS-441524 AUC₀₋₁₂ and C_{max}, respectively, between pediatric and adult participants, using 2 one-sided tests with each performed at an alpha level of 0.05. This power analysis assumes that the expected geometric mean ratio between the pediatric participants versus the adult group is 1, the equivalency boundary is 70% to 143%, and the interparticipant standard deviations of AUC₀₋₁₂ and C_{max} are 0.19 h•ng/mL and 0.18 ng/mL (natural log scale, preliminary results from Study GS-US-611-6248).

A sample size of at least 52 participants will provide a reasonable assessment of the safety profile of ODV.

Sample size and power calculations were made using the software package nQuery Advisor(R), Version 8.5.

9. RESPONSIBILITIES

9.1. Investigator Responsibilities

9.1.1. Financial Disclosure

The investigator and subinvestigators will provide prompt and accurate documentation of their financial interest or arrangements with the sponsor or proprietary interests in the study drug. This documentation must be provided before the investigator's (and any subinvestigator's) participation in the study. The investigator and subinvestigator agree to notify Gilead of any change in reportable interests during the study and for 1 year following completion of the study. Study completion is defined as the date when the last participant completes the protocol-defined activities.

9.1.2. Institutional Review Board/Independent Ethics Committee Review and Approval

The investigator (or Gilead as appropriate according to local regulations) will submit this protocol, ICF, and any accompanying material to be provided to the participant (such as advertisements, participant information sheets, or descriptions of the study used to obtain informed consent) to an IRB/IEC. The investigator will not begin any study participant activities until approval from the IRB/IEC has been documented and provided as a letter to the investigator.

Before implementation, the investigator will submit to and receive documented approval from the IRB/IEC for any modifications made to the protocol or any accompanying material to be provided to the participant after initial IRB/IEC approval, with the exception of those necessary to reduce immediate risk to study participant.

9.1.3. Informed Consent (or Assent)

The investigator is responsible for obtaining informed consent from parents and/or legal guardians as well as assent (age < 18 years, where locally and nationally approved) from each individual participating in this study after adequate explanation of the aims, methods, objectives, and potential hazards of the study before undertaking any study-related procedures. The investigator must use the most current IRB/IEC-approved ICF (or assent as applicable) for documenting written informed consent and assent. Each ICF (and assent as applicable) will be appropriately signed and dated by the participant or the participant's parent or legal guardian and the person conducting the consent discussion, and an impartial witness (if required by IRB/IEC or local requirements).

9.1.4. Confidentiality

The investigator must ensure that participants' anonymity will be strictly maintained and that their identities are protected from unauthorized parties. Only an identification code and any other unique identifier(s) as allowed by local law (such as date or year of birth, as applicable) will be recorded on any form or biological sample submitted to Gilead, IRB/IEC, or the laboratory. Laboratory specimens must be labeled in such a way as to protect participant identity while allowing the results to be recorded to the proper participant. Note: The investigator must keep a screening log with details for all participants screened and enrolled in the study, in accordance with the site procedures and regulations. Participant data will be processed in accordance with all applicable regulations.

The investigator agrees that all information received from Gilead, including but not limited to the IB, this protocol, eCRF, study drug information, and any other study information, remains the sole and exclusive property of Gilead during the conduct of the study and thereafter. This information is not to be disclosed to any third party (except employees or agents directly involved in the conduct of the study or as required by law) without prior written consent from Gilead. The investigator further agrees to take all reasonable precautions to prevent the disclosure by any employee or agent of the investigational site to any third party or otherwise into the public domain.

9.1.5. Study Files and Retention of Records

The investigator must maintain adequate and accurate records to enable the conduct of the study to be fully documented and the study data to be subsequently verified. These documents should be classified into at least the following 2 categories: (1) investigator's study file and (2) participant clinical source documents.

The investigator's study file will contain the protocol/amendments, eCRF, IRB/IEC, and governmental approval with correspondence, the ICF(s), drug records, staff curriculum vitae and authorization forms, and other appropriate documents and correspondence.

The required source data should include sequential notes containing at least the following information for each participant:

- Participant identification
- Documentation that participant meets eligibility criteria (ie, medical history, physical examination, and confirmation of diagnosis [to support inclusion and exclusion criteria])
- Documentation of the reason(s) a consented participant is not enrolled
- Participation in study (including study number)
- Study discussed and date of informed consent

- Dates of all visits
- Documentation that protocol-specific procedures were performed
- Results of efficacy parameters, as required by the protocol
- Start and end date (including dose regimen) of study drug, including dates of dispensing and return
- Record of all AEs and other safety parameters (start and end date; causality and severity) and documentation that adequate medical care has been provided for any AE
- Concomitant medication (start and end date; dose if relevant; dose changes)
- Date of study completion and reason for early discontinuation, if it occurs

All clinical study documents must be retained by the investigator for at least 2 years or according to local laws, whichever is longer, after the last approval of a marketing application in an ICH region (ie, the US, Europe, or Japan) and until there are no pending or planned marketing applications in an International Council for Harmonisation (ICH) region; or, if no application is filed or if the application is not approved for such indication, for 2 years after the investigation is discontinued and regulatory authorities have been notified. Investigators may be required to retain documents longer if specified by regulatory requirements, by local regulations, or by an agreement with Gilead. The investigator must notify Gilead before destroying any clinical study records.

Should the investigator wish to assign the study records to another party or move them to another location, Gilead must be notified in advance.

If the investigator cannot provide for this archiving requirement at the investigational site for any or all of the documents, special arrangements must be made between the investigator and Gilead to store these records securely away from the site so that they can be returned sealed to the investigator in case of an inspection. When source documents are required for the continued care of the participant, appropriate copies should be made for storage away from the site.

